#### **19.4.6 Response to Re-Treatment in Intermittent Arm**

The responses of PR, SD and PD will be summarised for the first, second, third etc. treatment breaks with an exact 95% CI.

#### **19.4.7 Time to next treatment for CLL**

Time from randomisation to next treatment after the cessation of trial treatment will be analysed using Cox regression analysis accounting for the stratification factors (excluding centre), and Kaplan-Meier curves will be presented. This analysis will seek to show the superiority of the intermittent strategy in this endpoint.

This endpoint, measuring time from registration, will also be summarised with Cox's regression and a Kaplan-Meier curves for the participants in the Clinical Need Cohort, stratified by MRD level, available from FLAIR.

#### **19.4.9 Rate of Resistance Mutation between Trial Arms**

The presence of BTK mutations (and other mutations, such as PLC- $\gamma$ 2 mutations) will be analysed at screening, 2 years, 4 years and when a participant progresses. The proportion of participants with such resistance mutations will be reported at screening (without a description of which arm the participant is randomised to) with a 95% confidence interval. In addition the rate of resistance mutation observed will be compared between the two randomised arms at 2 and 4 years post-randomisation. This comparison will be made using a 95% confidence interval for the difference in rates.

The proportion of participants with resistance mutations, with 95% confidence intervals, will be provided to the independent DMEC at these time-points. If there is a significant difference assessed by a 95% confidence interval, they will consider whether this should lead to the early reporting of the endpoint.

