### 6.3 Study Rationale

Ibrutinib is an extremely effective treatment for CLL with median progression-free survival (PFS) estimated to be 4 years in patients with a median of 3 prior lines of CLL therapy (4) and in excess of 10 years in newly diagnosed patients (3).

Ibrutinib is associated with long-term toxicities in a proportion of patients including arthralgia, bruising and bleeding, rashes and hypertension. Potentially serious side effects include cardiac arrhythmias, mostly atrial fibrillation but rarely ventricular tachyarrhythmias, and infections. It is hypothesised that toxicities may be reduced by an intermittent treatment approach.

A major concern with the chronic and continuous administration of ibrutinib is the selection of CLL sub-clones with BTK mutations leading to the development of disease resistance. Such BTK mutations are frequently observed in patients with relapsed/refractory CLL treated with ibrutinib and are also observed, but to a far lesser extent, in previously untreated patients receiving ibrutinib (6, 7). The emergence of these mutations is hypothesised to be reduced by intermittent use of the drug, as has been investigated using a similar strategy in prostate cancer (8).

We hypothesise that an intermittent treatment strategy with ibrutinib will reduce treatment-emergent resistance and thus be at least non-inferior to continuous treatment with regards to time to strategy failure whilst reducing resource impact for the NHS and improving quality of life. Recent work reveals the presence of BTK mutations is associated with drug resistance following continued treatment with ibrutinib in a third of patients with high risk CLL (9).

STATIC is designed with multiple pathways: the randomisation trial and the Clinical Need Cohort. The randomisation trial is designed to address the key question of whether an intermittent treatment

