#### 7.3.1 Hypothesis: Reduced Disease Resistance

We hypothesise that an intermittent treatment strategy using ibrutinib, will reduce treatment-emergent resistance and thus be at least non-inferior to continuous treatment with regards to time to treatment strategy failure whilst reducing resource impact for the NHS and improving quality of life.

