### 13.7.2 Baseline Central Investigations

The following samples are required from both randomisation arms (pausing ibrutinib and continuous ibrutinib arm) at baseline (these must be collected following registration, prior to randomisation):

- 20ml blood in EDTA to HMDS central laboratory for MRD flow cytometry, B-cell sorting, molecular BTK mutation analysis and for DNA/RNA storage
- 50ml anti-coagulated blood sent to UK CLL Biobank central laboratory
- Saliva Sample sent to the UK CLL Biobank central laboratory

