#### **17.4.10 Resistance Mutation**

The proportion of participants in each arm with a detectable BTK mutation (C481S and variant mutations or an alternative described resistance mutation such as the mutation of PLC- $\gamma$ 2) will be assessed at baseline, 24 months and 48 months for all randomised participants, and at 12, 36 months for those participants in whom a BTK mutation is detected.

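### The between-arm resistance comparison uses total mutation prevalence at 2 and 4 years and leaves out the baseline mutation result, so it reflects treatment-emergent resistance only in diluted, mixed form

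*Protocol*

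**What the plan says.** The hypothesis in protocol section 7.3.1 is that intermittent treatment "will reduce treatment-emergent resistance and thus be at least non-inferior to continuous treatment". Section 6.3 gives the same argument in terms of mutations emerging under continuous exposure.

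Section 17.4.10 defines the endpoint as "The proportion of participants in each arm with a detectable BTK mutation" or another described resistance mutation, which "will be assessed at baseline, 24 months and 48 months for all randomised participants". Section 19.4.9 sets the analysis. The baseline proportion "will be reported at screening (without a description of which arm the participant is randomised to) with a 95% confidence interval". For the arms, "the rate of resistance mutation observed will be compared between the two randomised arms at 2 and 4 years post-randomisation", and the method is given as follows: "This comparison will be made using a 95% confidence interval for the difference in rates". The DMEC receives the proportions with their intervals and, if the difference is significant, considers early reporting of the endpoint.

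The baseline result will exist. Section 13.7.2 requires a sample after registration and before randomisation, sent to the central laboratory "for MRD flow cytometry, B-cell sorting, molecular BTK mutation analysis and for DNA/RNA storage". None of the eligibility criteria in section 9 excludes carriers, and mutation status is not among the minimisation factors in section 10.5.1.

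**The concern.** Everyone randomised has already had long exposure to ibrutinib: at least 36 months for previously treated participants and 6 years for those from FLAIR (section 8.1). Section 6.3 describes BTK mutations as frequent in relapsed or refractory CLL on ibrutinib. Some participants may therefore carry a mutation when they are randomised, and section 19.4.9 itself plans to report how many.

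A carrier whose mutation persists counts as mutated at 2 and 4 years in either arm, although allocation did not cause that mutation. This shrinks the difference and adds noise. A carrier whose clone falls below detection during a pause counts as unmutated, although nothing was prevented. Section 19.4.10 allows for this, since it expects allele frequency on the intermittent strategy to hold steady or fall. A real reduction in emergence could be missed, or a difference produced by lost detection could be taken as evidence for the hypothesis. The DMEC would see the same interval.

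**Working it through.** The protocol states no size, power or precision for this endpoint, so there is no figure of its own to reproduce.

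**Inputs**
- From the protocol: 800 participants randomised 1:1, so 400 per arm.
- Assumed, because the protocol gives no values: baseline prevalence b from 0% to 30%; new mutations by the time point i₁ = 10% (continuous) and i₂ = 5% (intermittent); baseline mutations persist; all 400 per arm are sampled.

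**Planned comparison.** Prevalence in each arm is P = b + (1 − b)·i, so P₁ − P₂ = (1 − b)(i₁ − i₂). The standard error is √{[P₁(1 − P₁) + P₂(1 − P₂)]/400} and power is Φ(z − 1.96).

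At b = 10%, P₁ = 0.10 + 0.90 × 0.10 = 0.190 and P₂ = 0.10 + 0.90 × 0.05 = 0.145. The difference is 0.045, SE = √[(0.1539 + 0.1240)/400] = 0.0264, z = 1.71, power 40%.

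**New mutation in baseline-negative participants.** Here n = 400(1 − b) per arm and the rates are i₁ and i₂. At b = 10%, n = 360, the difference is 0.050, SE = √[(0.0900 + 0.0475)/360] = 0.0195, z = 2.56, power 73%.

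| Baseline prevalence | Prevalence difference (points) | Power, prevalence | n per arm, baseline-negative | Power, new mutation |
|---|---|---|---|---|
| 0% | 5.0 | 77% | 400 | 77% |
| 2% | 4.9 | 67% | 392 | 76% |
| 5% | 4.75 | 54% | 380 | 75% |
| 10% | 4.5 | 40% | 360 | 73% |
| 20% | 4.0 | 25% | 320 | 67% |
| 30% | 3.5 | 18% | 280 | 62% |

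With fewer sampled, power falls for both analyses but the pattern stays. At b = 10% it is 38% v 70% with 380 per arm and 31% v 60% with 300 per arm.

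**Stratifying by baseline status over all randomised participants.** With 380 per arm and b = 10%, the 95% interval for the prevalence difference is ±5.3 points unstratified and ±3.5 points stratified. At b = 2% it is ±4.1 v ±3.7.

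**Loss of detection.** Let new mutations be 10% in both arms, b = 10%, and half of the carriers in the intermittent arm become undetectable. Prevalence is 0.10 + 0.09 = 0.19 (continuous) against 0.05 + 0.09 = 0.14 (intermittent). The arms differ by 5.0 points with no difference in emergence. If one fifth of carriers clear instead, the gap is 2.0 points.

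**Chance imbalance at baseline.** The 95% range of the between-arm difference in carriers is ±1.96·√[2b(1 − b)/400]: ±3.0 points at b = 5% and ±4.2 at b = 10%. The planned comparison carries this noise in full.

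**The case against.** There are four arguments on the other side.

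- **The planned comparison does bear on emergence.** A reader might infer that it does not measure treatment-emergent resistance at all. That goes too far. Under randomisation, and if baseline mutations persist, the prevalence difference is (1 − b) times the difference in new mutations: diluted, but pointing the right way. This stands.
- **Baseline prevalence may be low.** Entry requires clinical remission for at least 12 months, and about 45% are expected from FLAIR, where section 6.3 expects far fewer mutations. A reader might take the statement that BTK mutations are "associated with drug resistance following continued treatment with ibrutinib in a third of patients with high risk CLL" as a guide to baseline prevalence. It describes resistance after continued treatment in high-risk patients, not carriage in a population selected for remission. A flat claim of large precision loss is therefore unsupported; only the conditional range is.
- **Total prevalence is a legitimate quantity.** Secondary objective 9 is the rate of resistance mutation between arms, and pausing might act on existing clones too. This stands as a reason to keep prevalence. It does not justify leaving out the baseline value.
- **Other provisions cover onset and clearance.** Participants with a detected mutation are also assessed at 12 and 36 months (17.4.10), biobank samples date the onset of sub-clones (17.4.11), and allele frequency is compared by strategy (19.4.10). These analyses concern people in whom a mutation is found. None gives a between-arm rate of new mutation.

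Section 19.4.9 also names no adjustment for FLAIR or MRD level, but that can be left to the statistical analysis plan and is not part of this point.

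**Conclusion.** The point holds in limited form. Sections 17.4.10 and 19.4.9 fix a comparison of total prevalence and give the pre-randomisation mutation result no part in it, while the hypothesis is about emergence. The result would be a diluted measure of emergence, mixed with persistence and possible loss of detection in carriers.

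The size depends on a baseline prevalence that the protocol does not state. On the assumed rates there is no loss at 0%, a modest one at 2% (67% v 76% power) and a large one from about 5–10% upwards (54% v 75%, then 40% v 73%). The false-signal scenario needs carriers to become undetectable more often when paused. The protocol allows for that but does not quantify it.

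This is one of ten secondary endpoints. The DMEC's action on it is to consider early reporting, and section 19.4.9 attaches no stopping rule to it. It is worth correcting because the data needed are already planned.

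**What to change.** In sections 17.4.10 and 19.4.9:

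1. Make the between-arm contrast a new resistance mutation by 24 and by 48 months among participants with no mutation in the baseline sample, with a 95% interval for the difference. Baseline status is fixed before allocation, so the comparison stays randomised.
2. Keep the overall prevalence difference as a supportive analysis, stratified by baseline mutation status over all randomised participants.
3. Report persistence or loss of the mutation in baseline carriers separately, by arm.
4. Give the DMEC the interval from item 1 as the basis for considering early reporting.

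The wording should say which samples count. Samples at restart (section 13.8.4) are taken in the intermittent arm only, so counting them would make detection unequal between arms.

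The cost is a change of text, with no new samples, visits or assays. The downside is a smaller denominator for the main contrast: 392 per arm at 2% baseline prevalence, 360 at 10% and 280 at 30%, if all 400 are sampled. On the assumptions above, power is still no lower than for the planned comparison at any baseline prevalence examined.

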### 13.8.2 Randomisation Pathway: Central investigations while on study

The following samples are required from both randomisation arms (pausing ibrutinib and continuous ibrutinib arm):

- 20ml in EDTA blood sent to HMDS at:
  - a. 24 months
  - b. 48 months
- 50ml anti-coagulated blood sent to UK CLL Biobank at:
  - a. 12 months
  - b. 36 months
  - c. 60 months
  - d. 72 months

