#### **13.8.4 Intermittent Treatment Strategy: Central Samples at Restart Criteria**

The following samples are required for participants who meet the restarting criteria:

- 20ml blood in EDTA to HMDS central laboratory
- 50ml anti-coagulated blood sent to UK CLL Biobank

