### 13.10.3 Central investigations

At treatment failure in the Randomisation Pathway for either arm (continuous or intermittent treatment arms) the following samples should be sent:

- 20ml blood in EDTA to HMDS central laboratory
- 50ml anti-coagulated blood sent to UK CLL Biobank

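### The 2- and 4-year comparison of resistance-mutation rates does not bring in the treatment-failure samples, so as written it rests on participants still on study

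*Protocol*

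**What the plan says.** Section 17.4.10 defines the endpoint as the proportion in each arm with a detectable resistance mutation, which "will be assessed at baseline, 24 months and 48 months for all randomised participants". Section 19.4.9 says mutations "will be analysed at screening, 2 years, 4 years and when a participant progresses", and then fixes the test: "the rate of resistance mutation observed will be compared between the two randomised arms at 2 and 4 years", by a 95% confidence interval for the difference. The same section sends these results to the DMEC, which is asked to consider early reporting if the interval shows a significant difference.

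The samples are scheduled as follows.

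- Section 13.8.2, which covers central investigations while on study, has "20ml in EDTA blood sent to HMDS at" 24 and 48 months.
- Section 13.10.3: "At treatment failure in the Randomisation Pathway for either arm (continuous or intermittent treatment arms) the following samples should be sent", followed by one HMDS and one Biobank sample.
- Section 13.11 has annual follow-up for three years after failure and names no central sample. Section 12.5 sends participants who have failed to off-study treatment.
- Appendix 4, HMDS row: entries at baseline, months 24/48 (in the 3-monthly visit column), restart and treatment failure. The column for follow-up after active disease is empty.
- Section 13.8.4, pausing arm only: "The following samples are required for participants who meet the restarting criteria", followed by HMDS and Biobank samples.

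**The concern.** A participant who fails or dies before month 24 or 48 has no sample at the compared time point, so the claim in 17.4.10 that all randomised participants are assessed then cannot be met. The loss is related to the outcome. The rationale in section 6.3 is that continuous ibrutinib selects resistant sub-clones and that relapse on the drug signals resistance, so those who leave through failure are the ones most likely to carry a mutation. A rate among those still sampled is a comparison of survivors, not of the randomised groups.

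The loss may also differ by arm. Under sections 8.1 and 13.8, active disease during a pause counts as failure only if it persists after ibrutinib is resumed; under section 12.5, active disease on continuous treatment counts at once.

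The endpoint matters because reduced treatment-emergent resistance is the mechanism behind the trial's hypothesis (section 7.3.1), and because the result may be reported early.

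**Working it through.** **1. Inputs (section 18.1).** 45% of participants from FLAIR with median PFS 10 years; 55% relapsed/refractory with median PFS 4 years; exponential within group; PFS as surrogate for strategy failure. 800 participants randomised 1:1.

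**2. Reproducing the plan's figure.** S(t) = 0.45 × 2^(−t/10) + 0.55 × 2^(−t/4). Setting S(t) = 0.5 gives t = 5.84 years, the stated overall median.

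**3. Share failed or dead at the compared times.**

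- 2 years: S = 0.45 × 0.871 + 0.55 × 0.707 = 0.781. Failed or dead 21.9%, about 175 of 800 (88 per arm).
- 4 years: S = 0.45 × 0.758 + 0.55 × 0.500 = 0.616. Failed or dead 38.4%, about 307 of 800 (154 per arm).

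These figures include deaths. If 30% to 50% of the events were deaths (assumed; the documents give no split), failures other than death would be 0.219 × 0.7 to 0.219 × 0.5 = 15% to 11% at 2 years, and 0.384 × 0.7 to 0.384 × 0.5 = 27% to 19% at 4 years.

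**4. When the sign can change.** Let F be the share failed (equal in both arms), q the mutation rate among those still followed and r the rate among those who failed. The all-randomised difference (pausing minus continuous) is (1−F)(q_p − q_c) + F(r_p − r_c). It has the opposite sign to a positive q_p − q_c when q_p − q_c < [F/(1−F)] × (r_c − r_p). The multiplier F/(1−F) is 0.219/0.781 = 0.28 at 2 years and 0.384/0.616 = 0.62 at 4 years.

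**5. Illustration with assumed constant hazards per year.** λ is mutation onset, g is failure or death from other causes, μ is the added failure hazard once mutated.

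- Alive, not failed, not mutated: N = exp(−(λ+g)t).
- Alive, not failed, mutated: M = λ exp(−gt)[exp(−λt) − exp(−μt)]/(μ−λ).
- Rate among those still sampled: M/(M+N).
- Cumulative incidence of mutation: [λ/(λ+g)][1 − exp(−(λ+g)t)].

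Example, t = 4, continuous arm, λ = 0.08, g = 0.06, μ = 1.0: N = 0.571, M = 0.048, rate 0.048/0.620 = 7.8%; cumulative (0.08/0.14) × 0.429 = 24.5%.

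Results at 4 years, continuous vs pausing (difference in points, pausing minus continuous):

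| Assumptions | Still sampled | Cumulative |
|---|---|---|
| λ 0.08 vs 0.05, g 0.06, μ 1.0 in both | 7.8% vs 4.9% (−2.9) | 24.5% vs 16.2% (−8.3) |
| same, μ 1.0 vs 0.3 | 7.8% vs 11.2% (+3.4) | 24.5% vs 16.2% (−8.3) |
| λ 0.08 vs 0.056, g 0.04, μ 0.5 in both | 13.4% vs 9.5% (−3.9) | 25.4% vs 18.6% (−6.8) |
| same λ and g, μ 1.5 vs 0.5 | 5.3% vs 9.5% (+4.2) | 25.4% vs 18.6% (−6.8) |

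With equal μ the direction is kept and the absolute difference roughly halves or worse. In the first set, equating the two still-sampled rates at 4 years puts the switch at a pausing-arm μ of about 0.56 against 1.0 on continuous; only below that does the sign reverse.

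The cumulative column counts true onsets. Counting failure samples recovers most of them, but not those in participants who die without a failure sample.

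**The case against.** The best defence is that the protocol can be read more kindly. Section 19.4 makes ITT the default for secondary endpoints, 17.4.10 speaks of everyone randomised, 19.4.9 lists progression among the analysis times, and a mutation found in an earlier failure sample could fairly be called observed by year 2 or 4. Nowhere is the denominator limited to those still sampled. The handling of missing samples could also be left to the SAP. This reading is possible, but it is not stated for the 2- and 4-year rates. The protocol itself fixes the times, population and method, and these conflict with its own schedule. Where it wants data after progression it says so, as it does for the questionnaires in 13.11 and Appendix 4.

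Four stronger conclusions are tempting, and the documents do not support them.

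- *The comparison will point the wrong way.* Reversal depends on exit hazards that no section gives; with equal hazards the direction is right, and the ratio (7.8/4.9 = 1.6) is close to the cumulative one (24.5/16.2 = 1.5).
- *22% and 38% are the biased share.* They include deaths, who could give no 24- or 48-month sample under any schedule, and failures who do give a failure sample.
- *Restart samples bias the plan.* They are taken in the pausing arm only, but neither 17.4.10 nor 19.4.9 lists them. The risk arises only if an analyst pools every available sample.
- *A significant interval triggers early release.* The DMEC is only asked to consider it, and the primary conclusion does not depend on this endpoint.

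**Conclusion.** The point holds as a mismatch between the stated comparison and the sampling schedule. The information from failed participants is collected and analysed, but the text does not carry it into the between-arm rates at 2 and 4 years. Read as written, those rates describe participants still on study.

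Under the protocol's PFS assumption, about 22% and 38% have failed or died by the two time points; failures other than death would be about 11% to 15% and 19% to 27% if 30% to 50% of events are deaths. The expected effect is a smaller absolute difference between arms, provided participants with a mutation do not leave faster on pausing than on continuous treatment. Reversal is possible but needs them to leave considerably faster on continuous treatment. The different failure rules for the two arms make that plausible, but the size is an assumption.

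This deserves correction because the endpoint tests the trial's stated mechanism and may be reported early. It is a secondary endpoint and does not affect the primary analysis.

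**What to change.** In 17.4.10 and 19.4.9, define the compared rate as cumulative detection of a resistance mutation by 24 and by 48 months among all randomised participants without one at baseline. Count scheduled and treatment-failure samples in both arms, and treat death without a detected mutation as a competing event. State that restart-only samples do not enter the between-arm comparison. Keep prevalence at 24 and 48 months among those sampled as a supportive result, with the number sampled in each arm. Reconcile the wording on all randomised participants in 17.4.10 with the HMDS row of Appendix 4. The change is best made before the DMEC sees the first 24-month comparison.

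The cost is protocol and SAP wording and a little more analysis work. No new samples or visits are needed.

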#### **19.4.10 Evolution of Resistant Sub-Clones**

In participants where a BTK mutation (or alternative resistance mutation) is observed the proportion of the CLL cells with the mutation will be studied and compared between the two treatment strategies. Annual samples will be studied to follow the variant allele frequency (VAF) of the mutant cells over time and by treatment strategy. This will be reported with 95% confidence intervals.

The effect of the treatment strategies will be assessed with a 95% confidence interval for the difference between the two groups. It might be expected that the VAF will increase in the continuous treatment arm but remain stable or even decrease in the intermittent treatment strategy. If a significant difference is detected then the DMEC will consider the early reporting of this endpoint.

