### 20.3 Data monitoring and ethics committee

An independent DMEC will review the safety and ethics of the study. The DMEC will review cumulative safety data by arm on an ongoing basis along with individual SAE/SAR listings. Detailed reports will be prepared by the CTRU for the DMEC meetings which will take place at approximately yearly intervals. The committee will also review the formal interim analyses detailed in Section 19.2.

Any interim reports provided to the DMEC will be provided by the CTRU Statistician and will be transferred securely as they contain research-sensitive data.

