### 22.2 Oversight / Trial monitoring groups

**Trial Management Group** - The TMG, comprising the Chief Investigator, CTRU team and co-investigators will be assigned responsibility for the clinical set-up, on-going management, promotion of the trial, and for the interpretation of results. Specifically the TMG will be responsible for (i) protocol

completion, (ii) eCRF/CRF development, (iii) obtaining approval from the REC and Health Research Authority (iv) submitting a CTA application and obtaining approval from the MHRA, (v) completing cost estimates and project initiation, (vi) appointing and facilitating the TSC and DMEC, (vii) reporting of serious adverse events to relevant parties, (viii) monitoring of screening, recruitment, treatment and follow-up procedures, (ix) auditing consent procedures, data collection, trial end-point validation and database development.

**Data Monitoring and Ethics Committee (DMEC)** - The DMEC will include independent membership and will review the safety and ethics of the trial by reviewing interim data throughout the trial. The Committee will meet or communicate via teleconference approximately annually. After each annual review, the DMEC will make their recommendations to the TSC about the continuation of the trial.

**Trial Steering Committee** - The Trial Steering Committee will provide overall supervision of the trial, in particular trial progress, adherence to protocol, participant safety and consideration of new information. It will include an Independent Chair, not less than two other independent members, and at least one patient representative. The Chief Investigator, Co-Chief Investigator and other members of the TMG will attend the TSC meetings and present and report progress. The Sponsor will also be invited to attend. The committee will meet annually as a minimum.

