## 23 PUBLICATION POLICY

---

The trial will be registered with an authorised registry, according to the International Committee of Medical Journal Editors (ICMJE) Guidelines, prior to the start of recruitment.

The success of the trial depends upon the collaboration of all contributors. For this reason, credit for the main results will be given to all those who have collaborated in the trial, through authorship and contributorship. Uniform requirements for authorship for manuscripts submitted to medical journals will guide authorship decisions. These state that authorship credit should be based only on substantial contribution to:

- *conception and design, or acquisition of data, or analysis and interpretation of data;*
- *drafting the article or revising it critically for important intellectual content;*
- *final approval of the version to be published;*
- *that all these conditions must be met ([www.icmje.org](http://www.icmje.org)).*

In light of this, the Chief Investigator, and relevant senior CTRU staff will be named as authors in any publication. In addition, all collaborators will be listed as contributors for the main trial publication, giving details of roles in planning, conducting and reporting the trial.

Publications will be sent to Janssen for courtesy review only ahead of submission with full independence and autonomy retained by the investigators and trial management group.

To maintain the scientific integrity of the trial, data will not be released prior to the end of the trial or a primary endpoint being reached, either for trial publication or oral presentation purposes, without the permission of the Trial Steering Committee and the Chief Investigator. In addition, individual collaborators must not publish data concerning their participants that is directly relevant to the questions posed in the trial until the main results of the trial have been published and following written consent from the Sponsor.

A summary of the study results and trial updates will also be shared with participants via the trial sites, patient forums, seminars and digital platforms, once the results have been published.

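### An unadjusted 95% interval triggers early reporting of the resistance endpoints, and the protocol does not fix when the looks take place

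*Protocol*

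**What the plan says.** Protocol section 19.4.9 states that "the rate of resistance mutation observed will be compared between the two randomised arms at 2 and 4 years post-randomisation", using a 95% confidence interval for the difference. The proportions, with 95% intervals, "will be provided to the independent DMEC at these time-points". The trigger follows: "If there is a significant difference assessed by a 95% confidence interval, they will consider whether this should lead to the early reporting".

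Section 19.4.10 sets a second trigger. "Annual samples will be studied to follow the variant allele frequency (VAF) of the mutant cells over time and by treatment strategy", the arms are compared with a 95% interval, and "If a significant difference is detected then the DMEC will consider the early reporting of this endpoint". The number of comparisons is not given.

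On oversight, section 20.3 says: "Detailed reports will be prepared by the CTRU for the DMEC meetings which will take place at approximately yearly intervals". Section 22.2 has the DMEC make recommendations to the TSC. Section 23 says that "data will not be released prior to the end of the trial or a primary endpoint being reached, either for trial publication" or oral presentation, unless the TSC and the Chief Investigator give permission.

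For the primary endpoint, section 19.3.1 sets a one-sided 0.25% level at the interim and 2.35% at the final analysis, to keep 2.5% overall. Nothing similar applies to the two resistance endpoints.

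**The concern.** A 95% interval has its nominal error rate when it is used once. Here the same interval is the prompt for early reporting at more than one time-point and for two endpoints, and no stricter level is reserved for the early look. The protocol allows for interim looks at the primary endpoint but not here.

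Reduced treatment-emergent resistance is the trial's stated hypothesis (sections 3 and 7.3.1). The trial is open-label, response is assessed by the local clinician (section 16), and clinicians or participants may alter treatment at their discretion (section 12.4). A false early report, in either direction, could appear while primary events are still accruing. It might then influence adherence or the calling of active disease in a non-inferiority comparison. That is a possibility; nothing in the protocol shows it would happen. In addition, an estimate released because its interval excluded zero tends to be exaggerated.

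**Working it through.** **Inputs from the protocol.** 95% interval as trigger; comparisons at 2 and 4 years (19.4.9); 1:1 allocation; 6 years of recruitment (8.1); final analysis about 3 years after recruitment closes (19.2.2); DMEC about yearly (20.3, 22.2). **Assumed, because the protocol does not give them:** mutation rates, correlation between the 2- and 4-year results, uniform recruitment, and the calendar timing of the looks.

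**The plan's own figure.** No error rate is stated for the resistance rule. For the primary endpoint, one-sided levels of 0.25% at half the information and 2.35% at full information (correlation √0.5 = 0.707) give 2.45% overall. The stated pair does hold 2.5%.

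**Two looks at the mutation rate.** Under no difference, P(at least one false trigger) = 1 − P(|Z1| < 1.96 and |Z2| < 1.96), with correlation ρ between looks. At ρ = 0 this is 1 − 0.95² = 9.75%.

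| ρ | Either direction | In favour of pausing |
|---|---|---|
| 0 | 9.75% | 4.9% |
| 0.5 | 9.1% | 4.5% |
| 0.71 | 8.3% | 4.1% |
| 0.9 | 7.0% | 3.5% |
| one look only | 5.0% | 2.5% |

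**Which ρ is plausible.** If mutations persist and the same participants are tested, ρ = √[p2(1 − p4) / (p4(1 − p2))], where p2 and p4 are the 2- and 4-year rates. For p2 = 10% and p4 = 20%, ρ = √(0.08/0.18) = 0.67. A binomial simulation with Wald intervals, assumed rates of 5-15% at 2 years and 10-30% at 4 years, and 300-400 per arm had ρ of 0.51-0.69. Its false-trigger rate was 8.3-9.3%.

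**Calendar timing.** Recruitment runs from year 0 to year 6.
- 24-month data accrue from year 2 to year 8.
- 48-month data accrue from year 4 to year 10.
- The final analysis is planned for about year 6 + 3 = 9.

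The error rate therefore depends on how the stated time-points are read:
- *One look on complete 2-year data (year 8):* 5% two-sided. Complete 4-year data would come only after the planned final analysis.
- *One look at each time-point:* about 7-10%, as above.
- *A cumulative test at each annual meeting (assumed):* 15.5% for the 2-year rate alone (6 looks, years 3-8). For both rates (11 tests, years 3-9) it is 20.4% at ρ = 0.9 and 27.5% at ρ = 0. In favour of pausing, these are about 8-14%. The year-9 tests coincide with the planned final analysis.

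**Two endpoints.** With a single look at each of the two resistance endpoints, the chance of at least one false trigger lies between 5% and 5% + 5% = 10%, depending on their correlation. No closer figure can be given, because section 19.4.10 does not state its number of looks.

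**Remedies.** One early look at 99.9% has a false-trigger rate of 0.1% per endpoint. Two looks at 97.5% give 1 − 0.975² = 4.94% if independent, and at most 2 × 2.5% = 5% in any case.

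**The case against.** A reader might infer that the DMEC can publish whenever an interval excludes zero, with a 16-28% chance of a false early claim. The protocol does not support this. The DMEC only considers early reporting and makes recommendations to the TSC, and section 23 requires permission from the TSC and the Chief Investigator. The percentages are chances of prompting a discussion, so they are upper bounds on a false report. The higher range also needs annual cumulative testing. Section 19.4.9 names 2 and 4 years. The word annual in section 19.4.10 describes samples, and the annual DMEC reviews in sections 19.2.1 and 20.3 cover safety and treatment-strategy data. Section 19.2.1 leaves report content to the SAP, which was not available.

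The other side can go further. On a complete-data reading, only the 2-year look is early, at 5%, with about one year to the final analysis. A false finding in favour of pausing has about half the two-sided probability. These are secondary endpoints, for which the protocol claims no family-wise control.

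All of that stands and limits the size of the point. It does not remove it. The protocol itself fixes the 95% interval as the trigger, so this is not detail left to the SAP. It does not fix the complete-data reading, and it reserves no stricter level for the early look. Section 23 adds a permission step but no statistical threshold, so the unadjusted interval is the only threshold those bodies are given.

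**Conclusion.** The concern holds in a limited form. Sections 19.4.9 and 19.4.10 prompt early reporting on an interval that takes no account of repeated looks or of two endpoints. With looks at both 2 and 4 years, the false-trigger rate for the mutation rate alone is about 7-10% two-sided (most plausibly 8-9%) against 5%, and about 3.5-4.9% in favour of pausing against 2.5%. This rests on assumed mutation rates and correlation, and it bounds the chance of a false early report from above. One look on complete 2-year data would bring it to 5%; about 15-28% applies only if the DMEC tests at every annual meeting, which the protocol does not state. The error rate of the primary non-inferiority test is not affected. The change is worth making, since it costs little and concerns the trial's stated hypothesis.

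**What to change.** In sections 19.4.9 and 19.4.10:
- Replace the 95% interval as early-reporting trigger with a stricter boundary, for example a 99.9% interval (Haybittle-Peto), at one pre-specified look, such as when all 24-month samples are in.
- Keep the 95% interval for the final analysis. For each comparison, the early look then adds at most 0.1 percentage point to the false-positive rate.
- State that, unless the boundary is crossed, by-arm resistance results stay with the DMEC until the primary analysis.

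If two looks are preferred, 97.5% intervals at each hold the total at or below 5% per endpoint; the calendar timing of both should then be stated.

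The cost is wording only. The downside is that a real but moderate difference in resistance would be reported with the primary result rather than earlier. If the early look waits for complete 24-month data, that delay is about one year on the planned timetable.
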